- b. Mechanical or bioprosthetic cardiac valve
- c. Pericardial constriction, effusion with tamponade physiology, or abnormal left atrial size.
- d. Restrictive or congestive cardiomyopathy
- e. Left ventricular ejection fraction ≤50% (measured in echocardiogram at screening)
- f. Symptomatic coronary disease
- g. Significant (2+ for regurgitation) valvular disease other than tricuspid or pulmonary regurgitation
- h. Acutely decompensated left heart failure within 1 month of screening
- i. History of untreated obstructive sleep apnoea
- 11. Evidence of significant lung disease on high-resolution CT (if available) or recent (performed within 12 months) lung function, where FEV1 < 50% predicted and FVC < 70% predicted, and DLCO (or TLCO) < 50% predicted if any CT abnormalities; judged by the Site Physician

- **12.** Patients with a history of uncontrolled systemic hypertension
- 13. Acute infection (including eye, dental, and skin infections)
- 14. Chronic inflammatory disease including HIV, and Hepatitis B
- **15.** Women of childbearing potential who are pregnant or breastfeeding (if applicable)
- 16. Previous intracerebral haemorrhage
- **17.** Patients who have received an Investigational Medicinal Product (IMP) within 5 half-lives of the last dose of the IMP or 1 month (which ever is greater) before the baseline visit
- *this does not apply to single antiplatelet therapy

TREATMENT:

There are two parts to the study. Part 1 will recruit 6 to 13 patients. The objective is to identify the highest tolerated dose. Part 2 will follow on. It will recruit a separate group of patients, up to 34, to evaluate the efficacy of the highest tolerated dose.

Patients will be invited to participate by one of the 8 NHS partner sites specialised in the management of PAH. Suitable patients will be treated with Imatinib once daily for up to 24 weeks. Patients will be asked to keep diaries for as long as they will be taking the study drug to ensure compliance.

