An interim analysis is planned after 13 patients have completed the 24-week treatment on the highest tolerated dose; some patients from Part 1 will be evaluable if they have completed 24 weeks on the highest tolerated dose. If there are 1 or no responses in these patients, the study will be stopped. Otherwise, additional patients will be recruited for a total of 34 evaluable patients (target for Part 2). The null hypothesis will be rejected if 7 or more responses are observed in the 34 patient cohort.

Blood levels of Imatinib will be measured in each patient at baseline and at the end of Weeks 4 and 24. A trough level (noting the time for last dose) will be measured at Week 4 and Week 24.

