4. INVESTIGATIONAL PLAN

4.1 Overall study design and plan

Patients will be invited to participate by their local designated pulmonary hypertension hospital. Suitable patients will be treated with Imatinib once daily for up to 24 weeks. The study is in two parts. The screening and consenting procedures are the same for Parts 1 and 2.

Part 1 will recruit 6 to 13 patients to identify the highest tolerated dose of Imatinib within the 100mg to 400mg per day range. This dose will then be used in Part 2 in a separate group of patients to assess efficacy according to the genes that relate to PDGF activity. It is necessary to find a single dose to maximise the opportunity to assess variation in response by genotype (i.e. reduce the influence of variation in exposure). It is necessary to find the highest tolerated dose to maximise the opportunity to capture a clinical response (i.e. reduce the chance of missing an effect). A starting dose of 100mg is based on experience from compassionate use; some patients, such as the case report above, have reported benefit from this dose. Doses of 200mg to 400mg daily were investigated in IMPRES (10) and many patients ended up on 200mg daily in the extension study. Our prior model of toxicity -see Section 10; skeleton- predicts that 200mg daily is likely to be the highest tolerated dose in PAH, and Part 1 is designed to explore this. A lower dose will be investigated in the efficacy phase if better tolerated.

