10. STATISTICS AND DATA ANALYSIS

Part 1 - Dose finding phase

The highest tolerated dose of Imatinib will be determined using a Bayesian continual reassessment method. An initial dose/toxicity skeleton was generated based on a one-parameter power model and a prior guess of toxicities based on expert opinion and data from the IMPRES trial (10) - see Figure 6. Patients will be recruited into the trial individually; the first patient will receive the lowest dose of Imatinib (100mg daily). The highest tolerated dose will be reassessed after each patient completes follow-up and recommended as the dose for the subsequent patient. Dose escalation between patients will be conducted in increments, with no patient receiving more than 100mg than the previous patient (within the 100mg-400mg dose range), guided by the previous dose administered using a statistical model and with oversight from an Independent Data Monitoring Committee. A safety stopping rule has also been imposed if the model identifies with 90% certainty that the lowest dose has a higher toxicity than the target toxicity level (TTL) of 20%. The minimum and maximum number of patients to enter Part 1 of the trial will be 6 and 13, respectively. Under these constraints, using simulation studies we have explored the operating characteristics of this trial design. If our prior toxicities hold true -see Figure 6- the trial design will correctly predict a dose within 10% of the TTL 90% of the time. After the 13th patient completes follow-up (or if a stopping rule is triggered or otherwise stopped early as described in section Premature Termination of the Trial) the toxicities and 90% credible intervals will be calculated for each dose level to generate the dose/toxicity quotient based on the data and prior experience from compassionate use. The highest tolerated dose will be recommended as the dose closest to 20% toxicity. We will also report SAE counts and toxicity incidence with or without withdrawal from study.

Extension phase

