The objective of Part 1 is to recommend a dose of imatinib for Part 2. While this is based on tolerability at 4 weeks, the inclusion of some patients with implanted CardioMEMSTM Heart Failure system and Fitbit activity monitor devices provides the opportunity to record the effect of imatinib on the pulmonary circulation and exercise capacity. These data can inform a harm-benefit assessment around the highest tolerated dose. To investigate this, 4 additional patients (patients 14 to 17) with an implanted CardioMEMSTM Heart Failure system and a Fitbit activity monitor will be recruited and treated with a dose of imatinib at or below the highest

PIPAH Study Page 38 of 47

tolerated dose suggested by the statistical model from Part 1 to gather further data to inform potential benefit. This approach is in line with recommendations from the independent Trial Steering and Data Monitoring (and Ethics) Committees who continue to provide oversight. Sequential recruitment is not required and enrolment of two or more patients in parallel is permitted in the extension phase.

Part 2 - Efficacy Phase

Treatment efficacy at the pre-determined highest tolerated dose will be assessed using a Simons two stage design. A null hypothesis that the true response rate is 0.10 will be tested against a one-sided alternative. The first stage interim analysis will happen after 13 patients have completed the 24-week treatment. If there are 1 or no responses# the study will be stopped. If there are 2 or more responses the trial will continue and recruit another 21 patients, creating a maximum sample size of 34 patients. After the final patient is recruited the null hypothesis will be rejected if 7 or more responses are observed. This design ensures a type I error rate of 0.042 and a power of 0.8034 when the true response rate is 0.27. The expected sample size under the null hypothesis is 21 and the probability of an early termination is 0.6213.

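### Part 1 completers may be counted in the Part 2 Simon test of a dose that their own haemodynamic response helped to choose, so the stated type I error of 0.042 is not assured

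*Protocol*

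**What the plan says.** **Who is counted.** The Study Summary (Treatment) says of Part 2: "It will recruit a separate group of patients, up to 34, to evaluate the efficacy of the highest tolerated dose". Section 4.1 also describes a separate group. The Part 2 paragraph of the same Summary says that "some patients from Part 1 will be evaluable if they have completed 24 weeks on the highest tolerated dose", and Section 4.1 tops recruitment up to 34 evaluable patients on that basis. The Summary caps the whole trial at 43 patients, with 6 to 13 in Part 1.

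**What sets the dose.** Section 10 (dose finding) gives a toxicity rule: "The highest tolerated dose will be recommended as the dose closest to 20% toxicity". Section 4.1 adds: "A lower dose will be investigated in the efficacy phase if better tolerated". The extension phase text in Section 10 refers to the pulmonary circulation and exercise data from Part 1 patients with implanted devices and says: "These data can inform a harm-benefit assessment around the highest tolerated dose". It then adds patients 14 to 17, treated at or below the model's dose, to gather information on benefit.

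**The test.** Section 10: "A null hypothesis that the true response rate is 0.10 will be tested against a one-sided alternative", and "This design ensures a type I error rate of 0.042 and a power of 0.8034 when the true response rate is 0.27". It calls the primary analysis intention-to-treat. Section 4.3.5 replaces discontinued patients.

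**The concern.** Two features can push the observed response rate upwards.

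1. **Selection on response.** If haemodynamic response helps to decide which dose goes forward, the patients on the chosen dose will on average look better than their true rate. Counting them again in the test of that dose carries this luck into stage 1.
2. **Selection on completion.** A Part 1 patient qualifies only by finishing 24 weeks on the chosen dose, which is when the response is measured. Patients who stopped early, and who may be less likely to respond, never enter the denominator.

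The trial is open-label and single-arm, so the Simon boundary is its only formal protection against a false positive. Section 10 says that the design ensures 0.042, but the calculation behind that figure treats all 34 patients as independent of the dose choice and unselected on outcome.

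**Working it through.** **Inputs from the protocol.** Null rate p0 = 0.10; alternative 0.27; n1 = 13, stop at 1 or fewer responses; n = 34, reject at 7 or more; Part 1 maximum 13; extension 4; cap 43.

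**Step 1: reproduce the design.**
- Early stopping under the null: 0.9^13 + 13 × 0.1 × 0.9^12 = 0.2542 + 0.3672 = 0.6213 (stated 0.6213).
- Expected size: 13 + (1 − 0.6213) × 21 = 20.95 (stated 21).
- P(reject) = sum over x = 2 to 13 of Bin(x; 13, p) × P(X2 ≥ 7 − x), with X2 ~ Bin(21, p). This gives 0.0420 at p = 0.10 and 0.8034 at p = 0.27, both as stated.

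**Step 2: does the headcount force overlap?** With a full Part 1 and 34 wholly new patients: 13 + 34 = 47, and 47 − 43 = 4. So at least 4 must be carried over. If patients 14 to 17 also fall under the cap: 17 + 34 = 51, and 51 − 43 = 8. Overlap is avoidable only if Part 1 has 43 − 34 = 9 patients or fewer.

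**Step 3: selection on response.** Assumptions: two candidate doses, m patients each, all with a true rate of 0.10; the dose with more responders goes forward and its m patients count among the 13. With F the Bin(m, 0.10) distribution function, the carried responders C have P(C = c) = F(c)² − F(c − 1)². The remaining 13 − m patients and stage 2 are unselected.

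Worked case, m = 2:

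| c | P(C = c), no selection | P(C = c), better of two | P(reject given c) |
|---|---|---|---|
| 0 | 0.8100 | 0.6561 | 0.0293 |
| 1 | 0.1800 | 0.3240 | 0.0899 |
| 2 | 0.0100 | 0.0199 | 0.2115 |

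The no-selection column gives 0.042. The better-of-two column gives 0.6561 × 0.0293 + 0.3240 × 0.0899 + 0.0199 × 0.2115 = 0.053. The same calculation gives 0.059 for m = 4, 0.064 for m = 6 and 0.067 for m = 8.

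If response decides half the time and toxicity otherwise, average with 0.042: (0.0420 + 0.0525)/2 = 0.047 for m = 2, and (0.0420 + 0.0673)/2 = 0.055 for m = 8.

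**Step 4: selection on completion, with no dose selection.** Assumptions: a share d of non-responders drops out and all responders complete. The rate among completers is q = 0.10 / (0.10 + 0.90 × (1 − d)), which is 0.122 at d = 20% and 0.137 at d = 30%. Apply q to the m carried patients and 0.10 to everyone else:

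| m carried | d = 20% | d = 30% |
|---|---|---|
| 4 | 0.048 | 0.052 |
| 6 | 0.051 | 0.058 |
| 8 | 0.055 | 0.064 |

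**Step 5: the benign case.** If toxicity alone sets the dose and every patient assigned that dose counts, with discontinuers as failures, the carried patients are ordinary draws and the type I error is 0.042.

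**The case against.** The strongest reply is that the only explicit dose rule is based on toxicity. The harm-benefit wording is permissive, and no passage picks the dose with most responders. Dose finding by continual reassessment also concentrates patients on one level, so two equal groups of 8 would need 16 of at most 17 patients. This stands: the figures in Step 3 are upper illustrations. It does not remove the point, because the text allows response data into the decision and has no safeguard against re-use.

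A second reply is that completer-only evaluation runs through Part 2 as well, because discontinued patients are withdrawn and replaced, and that the intention-to-treat label governs. The first half is fair, and Step 4 isolates only the carried-over part. The label does not settle the matter while the 13 and 34 are defined by completion or evaluability.

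Three stronger readings are tempting and are not supported:

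- **That toxicities in patients 14 to 17 never enter the dose model.** Section 10 places the final calculation after patient 13 (or an earlier stop), but excludes no later update, and Sections 4.2 and 10 describe updating after each patient. The protocol is silent here, which is not the same as a rule.
- **That patients 14 to 17 will be counted in Part 2.** Only patients from Part 1 are named. The amendment log calls the extension a Part 1 expansion, and the Summary allows monitor-based PVR in Part 1. Against that, these patients carry the device and are exempt from catheterisation, by which Section 4.1 measures Part 2 response. The text is ambiguous.
- **That a run of extension toxicities would overturn the recommended dose.** The skeleton figure is not shown, so any such example rests on an assumed curve. Three toxicities in four patients would also be improbable (about 1.6-2.7% at toxicity rates near the target).

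**Conclusion.** The point holds in a limited form. The protocol contradicts itself on whether Part 2 is a separate group. It admits Part 1 patients on completion, and it lets their response inform the dose without keeping them out of the test. The stated 0.042 is therefore not assured. The plausible inflation is modest: about 0.047-0.055 if response decides half the time, and up to 0.053-0.067 if it always decides between two doses. Completer-only entry by itself gives 0.048-0.064. These figures depend on assumed numbers of doses, carried patients and dropouts, and on dropout being confined to non-responders. With a purely toxicity-based choice and all assigned patients counted, there is no inflation. The use of patients 14 to 17, both in the test and in the dose model, is unstated.

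**What to change.** 1. **Define which Part 1 patients count.** For the 13 and 34, include every Part 1 patient first assigned the Part 2 dose, with discontinuers as failures, consistent with the intention-to-treat analysis in Section 10. Exclude those whose PVR or haemodynamic data were available to the dose decision, and report them descriptively. If this is not done, state that type I error is not controlled at 0.042 and give the recomputed range with its assumptions.
2. **Reconcile the text.** The Study Summary (Population and Treatment), Section 4.1 and Section 10 should agree on which patients count, which data set the Part 2 dose, and whether patients 14 to 17 count.
3. **State how extension toxicities are used.** Re-run the continual reassessment posterior on all patients, including these four, before the Part 2 dose is locked.

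**Cost.** Items 2 and 3 are wording and one model run. Item 1 may mean more new Part 2 patients. With a full Part 1, the cap of 43 could be exceeded by up to 4, or by up to 8 with the extension. At the 1 to 2 patients per month expected in Section 4.3, that is between 4/2 = 2 and 8/1 = 8 months. Where this is not acceptable, restating the error rate is the cheaper route.

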1. BACKGROUND AND RATIONALE

1.1 Pulmonary arterial hypertension (PAH)

PAH is an uncommon condition characterised by pre-capillary resistance to pulmonary blood flow in the absence of airway or parenchymal lung diseases, left heart failure or chronic thromboembolism (1,2). The resultant elevation in pulmonary artery pressure places an increased pressure load on the right ventricle, leading to right heart failure and premature death.

In around 50% of patients there is no identifiable underlying cause, and patients are classified as idiopathic PAH or, where there is a family history, heritable PAH. Histological examination of postmortem or transplantation PAH lung tissue shows marked pulmonary arterial remodelling with vascular cell proliferation narrowing the vascular lumen (3).

The estimated prevalence of PAH is 15 per million (2,4). It affects people in middle age and is an unmet clinical need. Five-year mortality for idiopathic/heritable PAH managed by experienced centres in the UK is around 58% (5). The current licensed treatments [prostanoids, endothelin receptor antagonists, phosphodiesterase type 5 inhibitors, and soluble guanylate cyclase stimulator] focus on pharmacologically manipulating 3 signaling pathways better known for regulating vascular tone (1,2,4). These treatments have little impact on the underlying vascular remodelling and do not arrest or reverse the course of the condition.

The past few years have seen attempts to target pulmonary vascular remodelling directly with antiproliferative or anti-inflammatory drugs (6). To date, the most promising data have come from studies with Imatinib (7-10); however, serious concerns over its safety and tolerability have limited its development as a treatment for PAH (11).

1.2 Imatinib

Imatinib is an orally active tyrosine kinase inhibitor (TKI) that inhibits platelet-derived growth factor receptor (PDGFR) alpha and beta, BCR-ABL, DDR and c-KIT (12). PDGF is a potent vascular smooth muscle cell mitogen (13). Studies of lung tissue from PAH patients and animal models indicate that PDGF is important in vascular smooth muscle proliferation and hyperplasia (6). Histological studies of human PAH lung show infiltration of pulmonary arterial lesions with c-kit(+) cells, which may also participate in vascular remodelling (14, 15). Imatinib consistently reverses pulmonary hypertension in experimental models (7).

These data are supported by two placebo-controlled randomised clinical trials; a Phase II involving 59 patients (9) and a Phase III including 202 patients (10) have provided evidence of clinical efficacy in PAH. The Phase III IMPRES study (10) reported a significant improvement in functional capacity (the mean placebo-corrected treatment effect on six-minute walk distance (6MWD) was 32m; 95% confidence interval, 12-52; P=0.002) and a reduction in pulmonary vascular resistance (PVR) of 379 dynes·s·cm⁻⁵ (95% confidence interval, −502 to −255; P<0.001, between-group difference) with Imatinib at 24 weeks compared to placebo in patients already receiving their licensed vasodilatory treatments (10). Unfortunately, Serious Adverse Events (SAEs) and discontinuations were more common in the Imatinib group (10).

Of particular concern, eight patients enrolled in IMPRES (10) developed a subdural haematoma while taking Imatinib, leading to death in two. These patients were taking an anticoagulant, warfarin, at the same time as Imatinib. An interaction between these two drugs is strongly suspected although the mechanism of this interaction is not known.

Despite these concerns, in the absence of alternative effective treatments, there remains considerable interest in the use of Imatinib for PAH. It is raised at all international meetings discussing PAH and drug development. As an indicator of clinical need, Imatinib continues to be used worldwide on compassionate grounds as a treatment of last resort and up to 100 patients may be taking it across Europe. Many specialist centres have case reports where patients have been 'rescued' by the drug.

Recent UK case study - April 2019

1.3 Targeting treatment with Imatinib - work to date

Patients with a diagnosis of PAH attend one of the UK centres that specialise in the management of PAH. Since 2013, we have recruited and followed a group of patients with idiopathic or heritable PAH as part of a cohort study (http://www.ipahcohort.com/). We currently have over 650 well-phenotyped patients with whole genome sequence data (21). We have plasma proteomic data (1,124 proteins using the aptamer-based assay from SomaScan) on 354 patients (22).

1.3.1 Expression of PDGFRB is influenced by common gene variant

A review of the literature shows three separate population-based studies that have identified a cisacting protein quantitative trait locus (pQTL) at PDGFRB for circulating levels of PDGFRB reaching genome-wide significance (P-value $<3\times10^{-113}$). We have reproduced this in our PAH cohort (rs2304058 variant, P-value $<1.88\times10^{-92}$) - see Figure 1.

[figure not shown]
Figure 1 - pQTL for PDGFRB

Further analysis shows a 1.6-fold increase in circulating PDGFRB levels per risk allele - see Figure 2. The difference between patients homozygous for the reference and risk alleles is approximately 3.5 standard deviations. If PDGFRB is an important target for Imatinib in PAH, PDGFRB genotype may

influence therapeutic response, or at least the dose required to elicit a response and the risk of dose-limiting side effects.

[figure not shown]
Figure 2 - Relationship of PDGFRB pQTL to plasma PDGFRB levels in PAH patients

1.3.2 Circulating proteins that track and/or predict response

Working with collaborators at Harvard (led by [name]), we accessed a protein-protein interactiome network (comprising around 350,000 protein-protein interactions connecting approximately 17,000 proteins) and mapped the proximity of the top 20 proteins associated with Imatinib -see Figure 3a- to proteins associated with PAH. Within this list were PDGFRB, ABL1 and ABL2, c-Kit and EGFR (ErbB1). We analysed paired plasma proteome data (measured in the SomaScan assay) from 14 patients treated with Imatinib for at least 6 months in IMPRES (10) and identified 166 proteins that changed in response to treatment (P<0.05 paired t-test). From a list of top 20 proteins from the proximity analysis, the change in circulating levels of c-Kit was statistically significant after false discovery rate correction and the change in levels of 2 other proteins, RET proto-oncogene, and mitogen-activated protein kinase 9, reached nominal significance - see Figure 3.

Figure 3 - (a) Protein network associated with Imatinib showing PDGFRB circled; (b) Change in plasma levels after Imatinib

Five of the 20 proteins from the proximity analysis (RAF1, Syk, IRAK1, ABCB1 and CLK1) are not on the 1,124 SomaScan platform. Interestingly, the plasma proteome analysis detected changes in the

circulating levels of 3 proteins (fibroblast activation protein-alpha/Seprase, and Stem Cell Growth Factor (alpha and beta) after false discovery rate correction that did not emerge from the proximity analysis; a working hypothesis is that the changes in levels of these proteins may indicate exposure to Imatinib but independent of any impact on underlying pathology of PAH.

2.60
Per 2.50
Per 2.50
Per 2.40
Responder

Oyes

No

No

2.30
-100.00 -75.00 -50.00 -25.00 .00 25.00

% change in PVR after Imatinib therapy

Figure 4 - Relationship of baseline ErbB3 to change in PVR post-Imatinib

We also investigated the relationship between baseline levels of proteins captured in the proteome analysis of 14 patients treated with Imatinib and response to the drug, assessed by change in PVR, and identified an association with plasma ErbB3 levels; low ErbB3 levels at the start of treatment were associated with a greater change in PVR - see Figure 4. This needs further validation. From this analysis, we suggest that the PDGFRB pQTL and/or a panel of proteins including c-Kit, RET, JNK2 and ERBB3 will inform the response of PAH patients to Imatinib.

